Official title: Synergistic effect of ^{18}F -FDG PET radiomics and International Prognostic Index on outcome prediction in diffuse large B-cell lymphoma

NCT number: 04317313

Document date: July 29, 2021

Study Protocol and Statistical Analysis Plan

Background: Previous studies have shown that ¹⁸F-FDG PET radiomics is predictive of survival in DLBCL. However, to the best of the investigator's knowledge, a multi-feature radiomic signature for prognosis assessment of DLBCL has not yet been described. Furthermore, it remains unclear whether PET-based radiomics could add more prognostic values to the IPI in DLBCL.

Objectives: This study aims to develop ¹⁸F-FDG PET radiomic signatures, and investigate whether the RS could improve the prognostic value of the IPI in predicting progression-free survival (PFS) and overall survival (OS) in DLBCL.

Study design and methods:

Study population

We retrospectively included patients with newly-diagnosed DLBCL between July 2013 and July 2019 in our institution. The inclusion criteria were: 1) histopathologically confirmed DLBCL, 2) over 18 years old, 3) underwent pre-treatment ¹⁸F-FDG PET/CT, and 4) initial treatment with R-CHOP (rituximab, cyclophosphamide, doxorubicin, vincristine, and prednisone) or R-EPOCH (rituximab, etoposide, prednisone, vincristine, cyclophosphamide, and doxorubicin). Patients were excluded if they had coexistent central nervous system lymphoma or second primary cancer, underwent surgical resection, or had an incomplete follow-up.

Clinical variables including gender, age at diagnosis, cell of origin, performance status, B symptoms, Ann Arbor stage, serum lactate dehydrogenase level, serum β 2-microglobulin (β 2-MG) level, extranodal involvement and treatment regimens of each patient were recorded. The IPI score was calculated.

Patient Treatment and Follow-up

Patients were initially treated with standard first-line chemotherapy every 21 days. Response to treatment was assessed according to the Lugano classification.

Follow-up was performed every 3 months after the completion of treatment, and ended in July 2021. The endpoints included OS (defined as the period from the initial diagnosis to the death from any cause) and PFS (defined as the period from the initial diagnosis to the progression, relapse or death from any cause).

PET Image Segmentation and Feature Extraction

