PET images were analyzed by two experienced nuclear medicine physicians who were blind to the patients' outcome. The volumes of interest (VOIs) were semiautomatically delineated using the LIFEx software (<https://www.lifexsoft.org/index.php>) with a fixed threshold of 41% SUVmax. A total of 1245 radiomic features were extracted via PyRadiomics software. The radiomics features consisted of four groups: (1) first-order statistics features; (2) shape descriptors features; (3) texture features calculated by gray level co-occurrence matrix (GLCM), gray level dependence matrix (GLDM), gray level run length matrix (GLRLM), and gray level size zone matrix (GLSZM); (4) filter and wavelet features obtained by filter and wavelet transformation of the original image, such as exponential, logarithm, square, square root and eight frequency band combinations (low-high-low [LHL], low-high-high [LHH], high-low-low [HLL], low-low-high [LLH], high-low-high [HLH], high-high-high [HHH], high-high-low [HHL] and low-low-low [LLL]).

Radiomics feature selection

First, intra-class correlation coefficients (ICCs) were used to evaluate the inter- and intra-observer agreement for 1248 features, including 3 conventional and 1245 radiomics features. Features with both inter- and intra-observer ICCs greater than 0.75 were retained. Then, the least absolute shrinkage and selection operator (LASSO) Cox regression algorithm with 10-fold cross-validation was applied to select the optimal features with non-zero coefficients in the training set. The radiomics signature was developed by linear combination of the selected features weighted by their respective coefficients. The cut-off value of the radiomics signature was identified by X-tile software. Based on the cut-off value of the R-signature, patients were divided into high-

and low-risk groups. Survival function of the R-signature was estimated by Kaplan-Meier analysis, and survival distributions were compared using log-rank test.

Model construction

Univariate Cox regression analysis was performed to investigate the prognostic value of the R-signature and clinical variables. Then, all significant variables were enrolled into a stepwise multivariate Cox regression to build an integrated radiomics-based model for PFS and OS prediction.

Model performance assessment

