Time-dependent ROC curve analysis was conducted to investigate the predictive accuracy of the R-signature, clinical variables and the integrated radiomics-based model. The 95% confidence interval (CI) of the area under the curves (AUCs) were calculated by bootstrapping with 1000 resampling. The AUC between the radiomics-based model and clinical variables was compared by using the Delong's test. The calibration plots and the Hosmer-Lemeshow test were used to compare the predicted and observed probabilities of the radiomics-based model. The decision curve analysis (DCA) was applied to determine the clinical utility by quantifying the net benefits under different threshold probabilities in the whole cohort.

Statistical analysis

The chi-square test and independent *t*-test were performed using SPSS software (version 25.0, IBM). ICC, LASSO regression analysis, time-dependent ROC analysis, Delong's test, calibration plots, Hosmer-Lemeshow test, DCA and Kaplan-Meier survival analysis were performed using R software (version 3.6.1, <http://www.r-project.org>). A two-sided *P* value of < 0.05 was considered statistically significant.

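### The objective is what the radiomics signature adds to the IPI, but no planned analysis is guaranteed to isolate that increment

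*Combined protocol and SAP*

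**What the plan says.** The Objectives section of the combined protocol and SAP says the study will "investigate whether the RS could improve the prognostic value of the IPI", for PFS and OS. The Background gives the same motive: "it remains unclear whether PET-based radiomics could add more prognostic values to the IPI in DLBCL".

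Under Study population, the recorded factors are introduced as "Clinical variables including gender, age at diagnosis, cell of origin, performance status, B symptoms, Ann Arbor stage, serum lactate dehydrogenase level", and the list continues with β2-microglobulin, extranodal involvement and regimen. The score comes in a separate sentence: "The IPI score was calculated". The sections on feature selection, model construction, model performance and statistical analysis do not mention the IPI again.

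Under Model construction, the RS and the clinical variables are screened one at a time by Cox regression, and the significant ones go into a stepwise Cox model. No term is forced in and no entry or removal rule is given. Under Model performance assessment, time-dependent AUCs are planned for the RS, the clinical variables and the integrated model. There is one formal comparison: "The AUC between the radiomics-based model and clinical variables was compared by using the Delong's test".

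**The concern.** The question is about an increment: what the RS adds once the IPI is known. It calls for a contrast between two models that differ only by the RS and share the IPI. The plan names no such contrast.

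Two analyses come close. The stepwise Cox model may yield an RS hazard ratio adjusted for the IPI, but only if selection keeps both. The plan also does not say whether the five IPI components in the clinical list (age, performance status, stage, LDH, extranodal involvement) compete with the score built from them. The DeLong test compares a whole model with a comparator whose form is not stated.

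At stake is the attribution of the main result. A gain over the IPI that comes partly from β2-microglobulin or cell of origin could be reported as the contribution of radiomics, with the plan followed to the letter.

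**Working it through.** **Step 1: planned analyses set against the objective.**

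| Planned analysis | Does it isolate RS given IPI? |
|---|---|
| Kaplan-Meier and log-rank by RS group | No, unadjusted |
| Univariate Cox | No, one variable at a time |
| Stepwise Cox | Only if both RS and IPI are retained |
| Separate AUCs with bootstrap intervals | No, accuracy of each rather than an increment |
| DeLong test | Not unless the comparator is the IPI and nothing else is retained beside IPI and RS |
| Calibration, Hosmer-Lemeshow | No, one model only |
| Decision curves | No comparator model named |

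The documents state no increment, sample size, event count or effect size, so there is no planned figure to reproduce. The numbers below are illustrations on assumed inputs. The plan supplies only the follow-up window: "We retrospectively included patients with newly-diagnosed DLBCL between July 2013 and July 2019 in our institution" and "Follow-up was performed every 3 months after the completion of treatment, and ended in July 2021". That gives July 2021 − July 2019 = 24 months at the shortest and July 2021 − July 2013 = 8 years at the longest.

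**Step 2: how often the stepwise model holds both terms.** Assumed: n = 150 or 250 (about 74 or 123 events); five binary components summing to the IPI, with equal or unequal prognostic weights; log hazard ratios per SD of 0.8 for the IPI, 0.5 for one other covariate and 0.3 for the RS; correlations 0.3; univariate P < 0.05, then stepwise by P value or AIC.

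- IPI score and RS both retained: 52–93% of runs across settings.
- RS dropped although its effect is real: 7–39%.
- IPI score missing when the RS is retained: 0–2% with equal component weights, 1–25% with unequal weights.

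The adjusted RS effect is often available but not assured. Loss of the IPI is the smaller part of the problem.

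**Step 3: what the AUC contrast contains if the comparator is the IPI.** Write Z for the other retained covariates. Then

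AUC(IPI+Z+RS) − AUC(IPI) = [AUC(IPI+RS) − AUC(IPI)] + [AUC(IPI+Z+RS) − AUC(IPI+RS)].

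The first bracket is the quantity in the objective. The second is what Z adds. Assumed: exponential survival, baseline hazard 0.13 per year, censoring uniform over 2–8 years, AUC at 2 years, log hazard ratios per SD of 0.8 (IPI) and 0.3 (RS), all correlations 0.3.

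With Z at 0.5: whole model minus IPI = 0.045 and IPI+RS minus IPI = 0.020, so Z supplies 0.045 − 0.020 = 0.025. The ratio is 0.045 / 0.020 = 2.25 (2.28 in a separate run).

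| Log hazard ratio of Z per SD | Apparent gain ÷ IPI+RS gain |
|---|---|
| 0 | 1.0 |
| 0.1 | 1.1 |
| 0.2 | about 1.3 |
| 0.5 | about 2.3 |

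**Step 4: dependence on the comparator.** With Z at 0.5, the same integrated model shows a gain of 0.045 over the IPI but 0.009 over its own terms refitted without the RS, a factor of 0.045 / 0.009 = 5. The plan does not say which kind of difference would be reported.

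**Step 5: which test can carry the inference.** If the RS adds nothing to the IPI, a nested likelihood-ratio test of IPI against IPI+RS rejected in 4.0–7.2% of runs, near the nominal 5% (assumed n = 150 or 300). For a real RS effect of 0.3, with IPI at 0.8 and Z at 0.5, the likelihood-ratio test detected it in 65% of runs at n = 150 and 86–87% at n = 250. DeLong's test, applied to the model with and without the RS in the same patients, detected it in 5.5–7.7% and 11–12%, and rejected in about 1% under a null RS. It is far too conservative for nested models fitted in the same patients.

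**The case against.** **The IPI comparison may already be intended.** The clinical factors are listed, the IPI follows in the next sentence, and the ROC sentence uses the same plural. A natural reading is one curve per variable, with the model tested against each, the IPI among them. This stands as a plausible reading, so the plan should not be said to omit the IPI as a comparator. It does not rescue the test, because the contrast is still whole model against IPI.

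**The multivariable Cox model already answers the question.** When both terms are retained it does give an adjusted RS effect, and on the assumed inputs that is the more common outcome. A reader might infer that the plan never adjusts the RS for the IPI; the text does not support that. What is missing is any assurance that both terms will be there.

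**The inflation depends on the inputs.** This also stands. A reader might infer that the reported gain would be about double the real one. That follows only if another covariate is stronger than the RS (0.5 against 0.3). If none is retained, the stepwise model is IPI+RS and the planned contrast against the IPI is the wanted one.

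**A worthless signature would not be credited.** Where the RS added nothing to the IPI and β2-microglobulin had a log hazard ratio of 0.5 per SD, the stepwise model beat the IPI by DeLong in 36.2% (n = 150) and 72.6% (n = 300) of runs. Those rates might be taken as false claims for radiomics. They are not: the RS stayed in the model in only 2.0–3.8% of runs across the settings tried, so its absence would be visible. A null signature may survive more easily if the Cox model reuses the patients in whom LASSO was run to "select the optimal features with non-zero coefficients in the training set". The plan does not say which patients are used, and that is a separate issue.

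**Conclusion.** The concern holds in a limited form. The objective is the increment of the RS over the IPI, and no planned analysis is sure to deliver it. One depends on the outcome of selection. The other has a comparator of unstated form and, even on the favourable reading, credits the whole model. This conclusion rests on the text alone.

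The size cannot be known from the documents. On the assumed inputs, the apparent gain over the IPI runs from 1.0 times the IPI+RS gain, with no other active covariate, through about 1.3 to about 2.3 times as that covariate's log hazard ratio goes from 0 through 0.2 to 0.5 per SD. Neither a doubling nor any minimum inflation above 1.0 should be quoted as a property of this study. The point should be fixed, but it does not make the study unusable.

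**What to change.** For PFS and OS separately, make the main analysis two nested Cox models with forced terms and no stepwise selection:

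- (a) the IPI score;
- (b) the IPI score plus the RS, entered as the weighted linear combination defined under Radiomics feature selection.

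Base inference on the likelihood-ratio test of (b) against (a) and on the adjusted hazard ratio of the RS with its interval. As a descriptive measure, report the change in time-dependent AUC, (b) minus (a), at a named horizon with a paired-bootstrap 95% interval. Two years is one choice that the recruitment and follow-up dates support.

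Make the comparison in patients not used to build the signature. If there are none, correct it for optimism or label it optimistic.

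Keep the stepwise model as secondary. In the AUC sentence under Model performance assessment, name the comparator. Do not use DeLong's test for nested models fitted in the same patients; report those AUC differences descriptively. State that this analysis was set after data collection.

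The cost is a change of SAP wording and four Cox fits (two models × two endpoints) with a bootstrap, on data already held. The drawbacks are that the reported gain may be smaller and that the analysis cannot be presented as set before data collection.

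### At any ROC horizon beyond 24 months, DeLong's test does not fit the censored PFS and OS data, and the plan names no horizon

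*Combined protocol and SAP*

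**What the plan says.** Under Study population, the cohort is "newly-diagnosed DLBCL between July 2013 and July 2019 in our institution". Patients who "had an incomplete follow-up" are excluded, but the term is not defined. Under Patient Treatment and Follow-up: "Follow-up was performed every 3 months after the completion of treatment, and ended in July 2021". Both endpoints are times to event counted from diagnosis, for example "PFS (defined as the period from the initial diagnosis to the progression, relapse or death from any cause".

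Under Model performance assessment: "Time-dependent ROC curve analysis was conducted to investigate the predictive accuracy of the R-signature, clinical variables and the integrated radiomics-based model". For precision: "The 95% confidence interval (CI) of the area under the curves (AUCs) were calculated by bootstrapping with 1000 resampling". For the comparison: "The AUC between the radiomics-based model and clinical variables was compared by using the Delong's test".

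The plan gives no horizon for the time-dependent ROC curves, no estimator for censored data, no rule for patients censored before the horizon, and no version of DeLong's test adapted to censoring.

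**The concern.** DeLong's variance is built from two fully observed groups, cases and controls, and has no term for censoring. A time-dependent AUC at horizon t needs to know who has had an event by t. Someone censored event-free before t belongs to neither group.

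To run the test at such a horizon, the analyst must either drop these patients or label them event-free, and the plan does not say which. Each choice defines an AUC that differs from a censoring-adjusted time-dependent AUC, so the P value and the estimate printed beside it may not refer to the same quantity.

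The study asks whether the radiomic signature improves on the IPI, and this is the plan's only formal test of an AUC difference. With the horizon and the handling of censored patients both open, the same data could yield several P values.

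**Working it through.** The plan states no sample size, event count or AUC, so there is no figure of its own to reproduce. The dates come from the plan. Accrual pattern, survival and marker effects are assumptions.

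**1. Potential follow-up.** July 2019 to July 2021 is 24 months; July 2013 to July 2021 is 96 months. The accrual window is 96 − 24 = 72 months.

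**2. Share whose potential follow-up is shorter than t**, with uniform accrual: (t − 24)/72.
- 24 months: 0%
- 36 months: 12/72 = 16.7%
- 48 months: 24/72 = 33.3%
- 60 months: 36/72 = 50.0%

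With accrual skewed 2:1 towards the early or the late years, the shares are 12-21%, 26-41% and 42-58% at 36, 48 and 60 months.

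**3. Share with unknown status at t** (censored before t and still event-free). This is the average of S(c) over follow-up times c between 24 and t. With a constant hazard λ it equals [S(24) − S(t)]/(72λ). With 22% events by 24 months, S(24) = 0.78, λ = −ln(0.78)/24 = 0.01035 and 72λ = 0.745.
- 36 months: (0.780 − 0.689)/0.745 = 12%
- 48 months: (0.780 − 0.608)/0.745 = 23%
- 60 months: (0.780 − 0.537)/0.745 = 33%

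Simulation with Weibull shapes 0.7 and 1.0 gives 12%, 23-24% and 33-35%. If 24-month event-free survival lies anywhere from 60% to 90%, with a constant hazard or one falling to a quarter after 24 months, the ranges are 9-15%, 16-30% and 21-44%.

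**4. What the two workarounds do under proportional hazards.** Simulation of 400,000 patients: 24-month event-free survival of 80% for a patient with average markers, log hazard ratios 0.8 and 0.5 per SD, horizon 60 months.

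| | Complete data | Unknown dropped | Unknown counted event-free |
|---|---|---|---|
| Event fraction | 46.3% | 60.8% | 41.6% |
| AUC, two-marker model | 0.789 | 0.795 | 0.779 |
| AUC difference from one marker | 0.0468 | 0.0473 | 0.0452 |

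Here 31.6% have unknown status, and 41.6/(100 − 31.6) = 60.8%. The event fraction moves a lot and the AUC difference very little. In a separate simulation of two unequal markers, the mean difference was 0.148 with complete data, 0.151 with dropping and 0.144 with counting as event-free. The largest shift across those settings was 0.005.

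**5. Test size.** With 150 patients (assumed), fixed scores, equal markers and administrative censoring only, DeLong's test rejected in 4.6-5.6% of runs at 36 and 60 months under either workaround, against 4.8-5.6% with complete data.

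**6. Marker effects that change during follow-up.** Administrative censoring after 24 months leaves early events over-represented among the observed cases. If a marker predicts early and late events differently, the forced-binary comparison is tilted towards the early effect. In simulations of this kind the AUC difference at 60 months was off by 0.018-0.037, while the inverse-probability-of-censoring-weighted (IPCW) difference was off by less than 0.002. The size depends on how strongly the effects change, about which the plan gives no information.

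**7. Precision.** At 60 months the SD of the AUC difference was 0.068-0.072 with IPCW and 0.067-0.072 with dropping in one simulation. In another it was 0.082 with IPCW, 0.080-0.081 with dropping and 0.067-0.071 with counting as event-free.

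**The case against.** **No horizon is stated, so the comparison may be made at 24 months or earlier.** This stands. Up to 24 months administrative censoring leaves practically nobody unknown. With 3-monthly visits, patients diagnosed in the last 3 months of accrual (3/72 = 4% under uniform accrual) might have their last PFS assessment slightly before 24 months. A reader might infer that the plan certainly applies DeLong's test to censored statuses; the text does not show that. It shows that nothing prevents it, with up to 96 months of follow-up available.

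**Patients with incomplete follow-up are excluded.** This does not settle the matter. If the phrase means loss to follow-up, administrative censoring remains. If it means not being followed to the horizon, those removed are all event-free, and the event fraction rises as in the dropped column above.

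**No harm to inference is shown.** Under proportional hazards with administrative censoring this is largely right: the size holds and the difference barely moves. It does not carry over to changing marker effects, which the plan gives no reason to rule out.

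**The remedy does not bring the missing patients back.** Correct. Patients censored event-free before the horizon get zero IPCW weight, so the contributing patients are the same as with dropping, only reweighted.

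**The question of added value does not rest on this test alone.** Also correct: the stepwise Cox regression under Model construction handles censoring and bears on the same question.

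**Conclusion.** The concern holds for any horizon beyond 24 months and should be addressed. The 24-month limit follows from the plan's dates alone. The unknown shares (roughly 12% at 36 months and 30-35% at 60) rest on uniform accrual and about 22% events by 2 years.

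The main defect is a P value not matched to a censoring-adjusted AUC, with the handling of censored patients left open. The numerical effect is about 0.005 or less on the AUC difference under proportional hazards and administrative censoring, and about 0.02-0.04 at 60 months if marker effects change over time.

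Two stronger readings are not supported. A reader might infer that DeLong's P value is wrong in general or that the comparison is badly biased; the calculations do not show this under proportional hazards, and the plan has no data showing which case applies. A reader might also infer that 24 months must become the primary horizon; the dates make it convenient, but nothing in the plan requires it.

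**What to change.** State the ROC horizon or horizons for PFS and for OS, and name the time-dependent AUC estimator. For any horizon beyond 24 months, replace DeLong's test with the difference in IPCW time-dependent AUCs between the integrated model and each clinical comparator. Give it a paired 95% CI, computing both AUCs in each of the 1000 bootstrap resamples already planned. Define the incomplete follow-up exclusion, so that a reader can tell who is censored and who is removed.

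Making 24 months the primary horizon is an option, at the price of fewer events than at later horizons.

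The cost is SAP wording, a few lines of code, and a slightly wider interval than counting censored patients as event-free would give. The gain is a test that refers to the reported AUC and is free of the bias from misclassified status. Lost patients and lost precision are not recovered.

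### DeLong's test is a weak, poorly calibrated test of whether the signature adds to the IPI; test the signature's coefficient in patients not used to build it

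*Combined protocol and SAP*

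**What the plan says.** The Objectives section asks whether the radiomic signature improves on the IPI for predicting PFS and OS. Three later sections determine how that is answered.

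- **Radiomics feature selection.** Agreement is first assessed for all candidates ("agreement for 1248 features, including 3 conventional and 1245 radiomics features"). LASSO Cox with 10-fold cross-validation "was applied to select the optimal features with non-zero coefficients in the training set". A cut-off is then chosen: "The cut-off value of the radiomics signature was identified by X-tile software".
- **Model construction.** After univariate screening, "all significant variables were enrolled into a stepwise multivariate Cox regression to build an integrated radiomics-based model for PFS and OS prediction".
- **Model performance assessment.** "The AUC between the radiomics-based model and clinical variables was compared by using the" DeLong test. Under Statistical analysis, a two-sided P "value of < 0.05 was considered statistically significant".

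The plan does not say which clinical variables form the comparator (IPI alone, each variable singly, or a clinical model), at what time point the AUCs are compared, or in which patients. It does not designate a likelihood-ratio test, or any other test of the signature's coefficient given the IPI, as the test of added value. Bootstrap intervals are planned for the AUCs, but none is described for their difference.

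**The concern.** When the stepwise step keeps the IPI, the comparison is between a model and a smaller model nested in it. DeLong's variance treats both scores as fixed and relies on the AUC difference being approximately normal. If the weights are estimated in the same patients and the signature adds nothing, its weight goes to zero and the two scores converge. The difference and its variance then shrink together, and the normal reference no longer applies. Against an integer score the effect is milder, because even a small weight breaks ties within an IPI level.

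The larger problem is sensitivity. A rank-based AUC difference responds weakly to a useful added term. Under nesting, a signature that adds nothing given the IPI leaves the AUC unchanged, so a test of its coefficient addresses the same null with far more power. A real gain over the IPI could be reported as not significant. In patients used to tune the signature the error runs the other way, and a signature of pure noise can be declared useful.

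**Working it through.** **Inputs from the documents.** Two-sided 5% level. Diagnosis July 2013 to July 2019 with follow-up ending July 2021, so potential follow-up runs from 24 months (July 2019 to July 2021) to 96 months (July 2013 to July 2021). Candidate features: 3 + 1245 = 1248, which agrees with the stated total. There is no sample size, event count, effect size or AUC, so there is no planned figure to reproduce. Everything below is Monte Carlo under stated assumptions.

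**Tests compared.**
- DeLong: z = (AUC_int − AUC_clin) / √(V_int + V_clin − 2·Cov), on 24-month status.
- Likelihood-ratio test (LRT): 2(ℓ₁ − ℓ₀) referred to χ² on 1 df. ℓ₁ contains the clinical score and the signature, ℓ₀ the clinical score only. It was run as a logistic model on the same 24-month status and as a Cox model on full follow-up.

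**Scenario A (assumed).** IPI 0–5 with HR 1.57 per point; signature fixed beforehand, HR 1.49 per SD, correlation 0.3 with the IPI; about 25–28% events by 24 months; all 24-month statuses known. Power, with results of separate runs separated by slashes:

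| n | DeLong | LRT, same 24-month status | Cox LRT |
|---|---|---|---|
| 100 | 12 / 13 / 10% | 46 / 46 / 48% | 71 / 71% |
| 150 | 23 / 18 / 19% | 62 / 62 / 66% | 88 / 88% |
| 300 | 43 / 43 / 56% | 90 / 92 / 92% | >99 / 99% |

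The spread for DeLong at n=300 shows that these should be read as ranges. With a null signature, DeLong rejected in 2.5–3.8% and the LRTs in 4.0–6.0%. With model weights taken from a separate sample (signature–IPI correlation 0 or 0.5), DeLong's size was about 5%, but its power at n=100–150 was still only 17–25%.

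**Scenario B (different assumptions).** Exponential survival with about 31% events at 2 years and 54% overall; integer score with HR 1.6 per point; correlation 0.3; signature binary (30% high) or continuous, since the plan does not say which form enters the model.

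| N, signature effect | DeLong | LRT, same 2-year status | Cox LRT |
|---|---|---|---|
| 150, binary HR 2 | 0.157 | 0.586 | 0.822 |
| 300, binary HR 2 | 0.355 | 0.879 | 0.979 |
| 150, HR 1.5 per SD | 0.235 | 0.701 | 0.921 |
| 300, HR 1.5 per SD | 0.532 | 0.946 | 0.999 |

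These effects raise the AUC by about 0.02–0.03 (for example 0.727 to 0.751, and 0.736 to 0.767). As a ratio of powers on identical data for binary HR 2, the shortfall is 1 − 0.157/0.586 = 73% at N=150 and 1 − 0.355/0.879 = 60% at N=300. Against a continuous clinical score (HR 1.8 or 2.5 per SD), DeLong's power was 0.099–0.413, with 0.585–0.947 for the LRT on the same status.

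With a null signature, DeLong's size was about 0.03–0.05 against the integer score and 0.011–0.018 against a continuous score. The Cox LRT stayed at about 0.044–0.059.

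**Where the gap narrows.** DeLong versus Cox LRT: 0.884 versus 1.00 (binary HR 3, N=400); 0.878 versus 1.00 (HR 2 per SD, N=250); 0.983 versus 1.00 (HR 2 per SD, N=400). For moderate effects at N=400 it is smaller but not closed: 0.467 versus 0.996 (binary HR 2) and 0.688 versus 1.00 (HR 1.5 per SD).

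**Tuned signature.** A LASSO Cox signature was built from 400 pure-noise features, with 160 replicates at each of N=100, 150 and 250. At least one feature was selected in 59, 66 and 54 replicates. Rejection rates in those replicates:

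| N | LRT, training patients | DeLong in favour of radiomics, training patients | LRT, independent patients | DeLong in favour of radiomics, independent patients |
|---|---|---|---|---|
| 100 | 0.983 | 0.356 | 0.085 | 0.000 |
| 150 | 0.985 | 0.439 | 0.000 | 0.000 |
| 250 | 0.981 | 0.667 | 0.074 | 0.019 |

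When the penalty grid always kept at least one feature, the training-set rates were 0.88–0.90 (LRT) and 0.24–0.33 (DeLong). With fewer features than the plan's 1248 and few replicates, these runs show direction rather than exact size.

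**The case against.** The strongest reply is that the stepwise Cox model already yields a coefficient for the signature adjusted for whatever clinical variables remain, so a non-significant DeLong result would not be the only evidence. Decision curves also speak to clinical utility. This stands in part: it would be too strong to infer that the study has no other evidence on its question. But that coefficient is reported after selection, the IPI need not be among the retained variables, and the plan does not name it as the test of added value.

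Other limits also stand.

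- **Nesting is conditional.** Screening or stepwise selection may drop a clinical variable. Against a dropped variable the models are not nested and the argument about a collapsing difference does not apply.
- **Undersizing is not general.** A reader might infer that DeLong's test is always too conservative here. Against an integer IPI, the comparator named in the Objectives, the shortfall is mild, and in training patients the direction reverses.
- **Missing most true increments is not general.** That depends on sample size and effect size, which the documents do not give.
- **An LRT on any patients is not the answer.** On training patients it is worse than DeLong's test.
- **Part of the Cox LRT's advantage is its use of full follow-up.** The fair comparison is the LRT on the same 24-month status, which still has far more power.

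**Conclusion.** The concern holds with conditions. Where the clinical comparator is retained and the signature was not tuned on the tested patients, DeLong's test is at or below its nominal level. For moderate increments at about 100–300 patients it has much less power than a coefficient test: 10–56% against 46–92% on the same 24-month status in Scenario A, and 10–53% against 58–95% at N=150–300 in Scenario B. The loss of power is the main harm and does not depend on undersizing. The gap narrows with large effects or N near 400. On LASSO training patients neither test is valid. Because the plan does not name the analysis set, it does not establish which situation applies. All sizes rest on the assumed sample sizes, event rates and hazard ratios. The documents do not support a claim that the test is undersized in every setting, or that it would miss most increments whatever the sample and effect.

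**What to change.** In Model performance assessment:

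1. Name the comparator (the IPI score), the time horizon and the patients in whom added value is tested.
2. Base the significance statement, separately for PFS and OS, on a 1-df Cox likelihood-ratio test of the continuous R-signature added to the IPI score.
3. Run it only in patients not used to select or weight the signature. Otherwise use cross-validated signature values with the whole LASSO step repeated within folds, and a P value that allows for the cross-validation, for example by permutation.
4. Report the AUC difference with a paired bootstrap interval as a description, and drop the DeLong P value.

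Cost: SAP wording and some re-analysis in R. The cross-validated route means rerunning the LASSO pipeline within folds, and again within each permutation if that is how the P value is obtained. A held-out subset has less power than the full cohort would, because the powers above apply to the number of patients actually tested. No new data are needed.
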